11.5. IDSMC

An Independent Data Safety Monitoring Committee (iDSMC) will be established to perform additional review of available safety data at regular intervals to ensure that the overall safety of the trial remains acceptable. The iDSMC will also have the opportunity to review toxicities observed over time, in cycles of treatment beyond the first cycle. Following each meeting, the iDSMC will provide in writing, recommendations to the Sponsor whether to continue, modify, or stop the study in compliance with the iDSMC Charter.

The iDSMC membership, data to be reviewed, timing of the planned reviews as well as the operating procedures will be described in the iDSMC charter.

12. DATA MANAGEMENT

Data management will be subcontracted to a CRO brafunder the supervision of the Sponsor's Data Manager of the IRPF Biometry Department.

All clinical data related to the study will be collected and saved in a computerized database according to the following procedures.

12.1. DATA COLLECTION

12.1.1. Electronic Case Report Form (e-CRF)

An e-CRF will be developed for this study. The electronic Case Report Form (e-CRF) will be used to record all subject data required by the protocol.

The e-CRF should be compliant with FDA regulations (Guidance for industry: Computerized systems used in clinical investigations 2007), European regulations (GCP guidelines – ICH E6 R2), compliant with 21CFR part 11 (electronic records and electronic signatures) and Japanese regulations, fully validated, and should include an access control and a traceability system for data corrections (audit trail).

Prior to the start of the study, the Investigator will complete a delegation form. The signature and initials of all persons in charge of e-CRF completion should be recorded on this form. Each person involved in e-CRF completion, review, correction and/or validation will be trained and will then have an individual login and access code to the e-CRF. An e-CRF user guide will be available for Investigators/on-site personnel involved in e-CRF completion and for CRAs.

All information entered into the e-CRF will be recorded from source documents by authorized personnel. The Investigator is responsible for the management and accuracy of the information entered into the e-CRF.

Each local assessment or examination (ECG, Laboratory samples, Questionnaires, ...) will be entered into the appropriate e-CRF forms by the designated investigational site staff at each site. An e-CRF must be completed for each subject enrolled in the study (i.e. signed ICF).

12.1.2. Pharmacokinetics data

Actual dates and times of blood collections for study treatments dosing will be entered in both the e-CRF and the requisition form. Appropriate dates and times of study treatment intake will be entered in the e-CRF. The samples will be sent to a designated CRO for analysis.

Validated results from bioanalysis of treatments concentrations in plasma or serum will be transmitted by the bioanalytical center to the sponsor or designated CRO. The study treatment

concentrations will be uploaded in the final database from an electronic data file provided by the bioanalytical laboratory.

12.1.3. Biomarkers

Dates and actual times of biomarker samples will be entered in both the e-CRF and the requisition form.

***BRAF*^{V600E} mutation status:** is assessed by local laboratory and/or by central laboratory. Results from central laboratory will be sent to each site for validation of local result. The result from local laboratory will be entered by the designated investigational site staff at each site into the e-CRF as well as the confirmation provided by the central laboratory. The result from the central laboratory will be provided with an electronic data file.

Other biomarkers: The samples will be sent to sponsor or a designated CRO for analysis. If any of the biomarker analyses are intended to form part of the CSR, they will be transferred to the data management CRO for validation and integration into the study database.

CEA, CA 19-9: are assessed by local laboratory, and data will be entered into the appropriate e-CRF forms by the designated investigational site staff at each site.

12.1.4. Imaging

Local assessment (Main study and Study extension periods): scans will be assessed by local radiologists at the sites and RECIST measurements will be entered into the appropriate e-CRF forms by the designated investigational site staff at each site.

Central assessment (Main study period only): scans will then be submitted for a centralized review. The central imaging reader will review the scans and results will be provided with an electronic data file to the CRO.

12.2. DATA CLEANING

The Data Manager will define descriptions of manual and electronic edit checks in the study Data Validation Plan for reviewing and querying data. Upon approval, the edit checks and listings will be programmed.

The Data Manager will follow the cleaning of the data over the course of the study. The Investigator will be asked to resolve queries by making changes directly into the e-CRF. The system's automatic audit trail will record the date, time and author of the changes.

12.3. DATA CODING

AEs, concomitant diseases, medical/surgical histories will be coded using MedDRA dictionary (latest version in use).

Prior and concomitant medications will be coded using WHO-DRUG dictionary (latest version in use).

The coding will be validated by a physician.

12.4. DATABASE LOCK

The validated database will be locked upon request of the Sponsor's Data Manager following the completion of all required steps, i.e.: entry, reception and check of all data, resolution of all queries, validation of the coding, Clinical and Pharmacovigilance database reconciliation, and data review / validation committee meeting performed.

12.5. DATA STORAGE

Data and any modifications will be saved and kept available upon request of the Sponsor. The Sponsor's Data Manager will assume storage of the locked clinical database in SAS format on a secured server.

Electronic capture of all e-CRFs will be sent in PDF format to the Sponsor, and then stored on a dedicated secured server by the Sponsor.

A CD-ROM containing the PDF version of all e-CRFs of the site (including audit-trail) will be archived by the investigational site.

13. STATISTICAL ANALYSIS

13.1. GENERAL CONSIDERATIONS

A detailed statistical analysis plan (SAP) will be prepared by the Sponsor. This plan may modify the statistical methods outlined in the protocol; however, any major modifications related to the primary outcome measure definition or analysis will also be described in a protocol amendment.

The statistical analysis will be done under the supervision of the study statistician at the Biometry Department, IRPF. Analyses will be programmed in accordance with the SAP.

The CSR is planned to be written at the time of the primary outcome measure analysis (after Stage 1 if the study is stopped for futility, otherwise after Stage 2).

The cut-off date for futility analysis and Stage 2 analysis is estimated to occur approximately when all treated subjects with a centrally confirmed *BRAF*^{V600E} mutation of the concerned stage have either discontinued or have four post-baseline tumor assessments. And in case the last subject required for the concerned stage has an objective response, it should be confirmed in the following tumor assessment before the analysis is being performed. However, it will be possible to proceed to Stage 2 as soon as 40 subjects with a centrally confirmed *BRAF*^{V600E} mutation are treated and 12 confirmed responses are observed.

All available data will be included at the time of the cut-off date for secondary time-to-event endpoints and safety assessments. Unless the study is stopped at an earlier point in time, any further CSR update (or addendum) will be written at the end of study.

After the primary outcome measure analysis (after Stage 1 if the study is stopped for futility, otherwise after Stage 2), an analysis will be performed at the end of the Main study period, and at the end of the Study extension period).

Descriptive methods will be used to present all relevant data:

- Continuous data will be summarized with: frequency, median, range, mean, standard deviation and standard error if relevant.
- Categorical data will be presented in contingency tables with frequencies and percentages of each modality.

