Statistical Methods:	
Sample Size Determination
 
The sample size is based on a two-stage design with nominal alpha=2.5% and beta=20%. The null hypothesis that the true response rate is 30% (maximum unacceptable probability of response) will be tested against a one-sided alternative. In the first stage, 40 subjects will be treated. Subjects in whom the presence of BRAF^{V600E} is not confirmed by central laboratory will be replaced. If there are 11 or fewer confirmed responses in the 40 treated subjects with a centrally confirmed BRAF^{V600E} mutation, inactivity will be declared and the study will be stopped for futility.
 
The time point for the futility analysis will be after all 40 treated subjects of stage 1 with centrally confirmed BRAF^{V600E} mutation had the opportunity to complete four post baseline assessments and after subjects with an initial objective response have had an opportunity to have a confirmation scan. However, it will be possible to proceed to Stage 2 as soon as 40 subjects with a centrally confirmed BRAF^{V600E} mutation are treated and 12 confirmed responses are observed.
 
Subjects data that will be analyzed during the futility analysis will be reviewed on an ongoing basis in order to determine as soon as possible (even before the inclusion of the 40th subject) whether the criteria for continuing to stage 2 (12 confirmed responses) are satisfied or not.
 
As it may take several treatment cycles for subjects to achieve a confirmed response, a limited number of subjects (maximum 12) from stage 2 may be treated while waiting for all subjects in the initial cohort of 40 subjects in Stage 1 to be evaluable for a confirmed response providing no safety concern was raised by the iDSMC. These additional subjects will not count towards responses in Stage 1 but will be included as part of the Stage 2 cohort, should the study move forward into Stage 2.
 
If at any time it becomes evident that the threshold of 12 responses is unlikely to be met, then additional subjects may not be recruited (eg: 6 or fewer responses among 35 subjects with sufficient follow up [potential for at least 2 assessments]). If the study continues to the second stage, 50 additional subjects will be treated for a total of 90. Subjects in whom the presence of BRAF^{V600E} mutation is not confirmed by central laboratory will be replaced. The null hypothesis will be rejected if 37 or more confirmed responses are observed in 90 treated subjects with a centrally confirmed BRAF^{V600E} mutation. This design yields a 1-sided type I error rate of 1.6% and power of 80% when the true response rate is 45%.
 
The cut-off for stage 2 analysis will be after all 90 treated subjects of stage 1 and 2 with centrally confirmed BRAF^{V600E} mutation had the opportunity to complete four post-baseline tumor assessments, and after subjects with an initial objective response have had an opportunity to have a confirmation scan.

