13.3. SAMPLE SIZE

The sample size is based on a two-stage design with nominal $\alpha=2.5\%$ and $\beta=20\%$. The null hypothesis that the true response rate is 30% will be tested against a one-sided alternative. In the first stage, 40 subjects will be treated. In case of discordance in the results between the local assay and the central laboratory (potential false-positive local result), or lack of BRAF^{V600E} confirmation, subject will be replaced. If there are 11 or fewer confirmed responses in the 40 treated subjects with a centrally confirmed BRAF *BRAF*^{V600E} mutation, inactivity will be declared and the study will be stopped for futility.

If the study continues to the second stage, 50 additional subjects will be treated to achieve a total of 90 subjects. In case of discordance in the results between the local assay and the central laboratory (potential false-positive local result), or lack of *BRAF*^{V600E} confirmation, subject will be replaced. The null hypothesis will be rejected if 37 or more confirmed responses are observed in 90 treated subjects with a centrally confirmed *BRAF*^{V600E} mutation. This design yields a 1-sided type I error rate equal to 1.6% and power of 80% when the true response rate is 45%.

The sample size calculation was based on binomial probabilities calculated in R (version 3.2.3).

This binomial design matches the O'Brien-Fleming design (**O'Brien, 1979**) for one sample obtained using East software (version 6.4) with a 1-sided type I error rate equal to 2.5% and a power of 81%.

If 37 confirmed responders are observed in 90 subjects, the Clopper-Pearson (exact) binomial 95% confidence interval would be [30.8%, 52.0%] with the lower limit exceeding the clinically relevant response rate of 30%.

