Given the sparse PK sample collection, PK parameters for encorafenib, binimetinib and the active metabolite of binimetinib (AR00426032) and cetuximab may be generated by a compartmental approach such as a population approach, as appropriate. Details of these analyses and of the incorporation of prior information to support the model building will be provided in a specific standalone modeling plan. Analyses will be provided in a separate report.

Relationships between PK and biomarkers, clinical response and/or safety will be explored if appropriate and if data quality is adequate. Details of analyses will be included in a specific standalone modeling plan and results will be reported separately.

13.15.INTERIM ANALYSIS

The two-stage design involves an interim analysis to allow for the possibility of stopping the study early for futility.

The interim analysis of the cORR is planned and based on the 40 treated subjects from stage 1 of the study.

The time point for the futility analysis will be after all 40 treated subjects of stage1 with centrally confirmed *BRAF*^{V600E} mutation had the opportunity to complete four post baseline tumor assessment. And in case last subject required for the futility analysis has an objective response, it should be confirmed in the following tumor assessment before the futility analysis is performed.

However, it will be possible to proceed to Stage 2 as soon as 40 subjects with a centrally confirmed *BRAF*^{V600E} mutation are treated and 12 confirmed responses are observed.

Subjects data that will be analyzed during the futility analysis will be reviewed on an ongoing basis in order to determine as soon as possible (even before the inclusion of the 40th subject) whether the criteria for continuing to stage 2 (12 confirmed responses) have been met.

As it may take several treatment cycles for subjects to achieve a confirmed response, if 12 confirmed responses are not observed at the time the 40th subject is treated in Stage 1, a limited number of subjects (maximum 12) subjects from stage 2 may be treated while waiting for all subjects in the initial cohort of 40 subjects in Stage 1 to be evaluable for a confirmed response providing no safety concern was raised by the iDSMC. They will not count towards responses in Stage 1 but will be included as part of the Stage 2 cohort, should the study move forward into Stage 2.

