If at any time it becomes evident that the threshold of 12 responses is unlikely to be met, then additional subjects may not be recruited (eg: 6 or fewer responses among 35 subjects with sufficient follow up [potential for at least 2 assessments]).

If 11 or fewer confirmed responses are observed in subjects with centrally confirmed *BRAF*^{V600E} mutation in stage 1, the treatment will be deemed not efficacious. Inactivity will be declared and the study will be stopped for futility.

If 12 or more confirmed responses are observed in stage 1, 50 additional subjects with a centrally confirmed *BRAF*^{V600E} mutation have to be treated. The cut-off for stage 2 analysis will be after all 90 treated subjects of stage 1 and 2 with centrally confirmed *BRAF*^{V600E} mutation had the opportunity to complete four post-baseline tumor assessments, and after subjects with an initial objective response have had an opportunity to have a confirmation scan.

An SC will review the primary outcome and safety data for the interim and final analyses (see **Section 11.4**).

An iDSMC will review the available safety information at regular interval (see **Section 11.5**). Analyses for iDSMC will be based on safety, thus this will not affect the statistical operating characteristics of the Stage 1 and Stage 2 analyses.

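### Two cut-off rules coexist for the confirmed-response analyses: one waits for a confirmation scan only if the last subject responds, the other for every initial responder

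*Protocol*

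**What the plan says.** Two rules appear in the current text.

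**Last-subject rule.** Protocol 13.1 (General considerations) and SAP 6.6 (Cut-off dates) apply it to both the futility and the stage 2 analysis. Once the stage's subjects have had four post-baseline assessments, the analysis is held back further on one condition only: "in case the last subject required for the concerned stage has an objective response, it should be confirmed in the following tumor assessment". SAP 6.5 repeats this for futility. Protocol 13.15 (Interim analysis) has the same condition for futility: "in case last subject required for the futility analysis has an objective response".

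**All-responder rule.** The protocol synopsis, for both analyses, sets the time point after four assessments and "after subjects with an initial objective response have had an opportunity to have a confirmation scan". The stage 2 paragraphs of Protocol 13.15 and SAP 6.5 use the same wording.

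Each analysis therefore has two answers, and Protocol 13.15 and SAP 6.5 each change rule between stages.

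Three further provisions decide the consequence. Main-period scans are every 6 weeks to week 12 and every 8 weeks after that (flow-chart, Protocol 8.1). SAP 14.1 requires two determinations at least 4 weeks apart for a confirmed response, and Table 10, case 15 codes a single unconfirmed response at 6 weeks or later as stable disease. SAP 9.5 keeps data obtained after the cut-off out of listings and summaries.

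**The concern.** A programmer looking for the cut-off goes first to SAP 6.6, which carries the narrower rule for the primary analysis. Read literally, that rule lets the data be cut while other subjects' responses still await confirmation. Those subjects stay in the denominator as non-responders because of where they fall in the enrolment order. The decision is a fixed count, 37 of 90, so one response can change it. Repeating cORR at the end of study (SAP 14.1.1) would recover late confirmations for estimation, but it does not replace the stage 2 test.

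**Working it through.** **Who is affected.** Scheduled scans fall at weeks 6, 12, 20, 28 and 36, so the fourth is at week 28. Let the last required subject start at time S and have no response awaiting confirmation. The literal cut-off is then S + 28 weeks. A subject who started d weeks before S is at week 28 + d at that point:

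- First response at week 6, 12 or 20: the next scan is at week 28 or earlier, so it has been done.
- First response at week 28, d of 8 or more: the week-36 scan has been done.
- First response at week 28, d below 8: the week-36 scan is still to come, so Table 10, case 15 gives stable disease.

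The ±7-day windows blur the 8-week limit slightly. A subject whose scheduled confirming scan was missed or not evaluable can be caught in the same way. If the last subject is itself awaited, earlier starters will normally have had their week-36 scan as well.

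**Reproducing the design (Protocol 13.3).** The inputs are 40 subjects in stage 1, continue at 12 or more, 50 further subjects, and reject at 37 or more of 90. The probability of rejection is

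Σ (x = 12 to 40) P(X₁ = x; 40, p) × P(X₂ ≥ 37 − x; 50, p).

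- p = 0.30: 0.0161 (stated 1.6%).
- p = 0.45: 0.7985 (stated 80%).
- Clopper-Pearson interval for 37/90: 30.8% to 52.0%, as stated.

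**Effect of m true responders left uncounted at the final test.** This is the same as needing 37 + m:

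| m | Type I error at 30% | Power at 45% |
|---|---|---|
| 0 | 1.61% | 79.8% |
| 1 | 0.92% | 73.5% |
| 2 | 0.50% | 66.2% |

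A lost response changes the decision when the true count is exactly 37. At a 45% rate, P(37 of 90) is 6.5%, in line with the drop of about 6 points for m = 1. At that boundary, 37/90 (lower limit 30.8%) would be recorded as 36/90 (lower limit 29.8%), and the conclusion reverses. The matching stage 1 cell is 12 of 40, with probability 2.1% at 45%. One uncounted responder there raises the chance of a false stop from 1.8% to 3.9%.

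**How many might be uncounted (illustration only).** The documents give neither the share of responders who first respond at the fourth scan nor the accrual curve. Assume uniform accrual of 90 subjects over about 60 weeks (November 2018 to 27 December 2019): 90/60 × 8 = 12 subjects start within 8 weeks of the last. With a share f of responders first responding at scan 4, the expected number uncounted is 12 × 0.45 × f. The power column also assumes 5 late starters at futility.

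| f (assumed) | Expected uncounted | Power at 45% |
|---|---|---|
| 5% | 0.27 | 78.2% |
| 10% | 0.54 | 76.5% |
| 20% | 1.08 | 72.9% |

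Faster late accrual would enlarge the loss. With 20 late starters in stage 2 and 8 at futility, power is 77.1%, 74.1% and 67.6%.

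**The case against.** The strongest reply is that the two rules are compatible. The last-subject sentence adds a wait; it does not order the analysis to proceed while other responses are open. Waiting for every initial responder satisfies both texts, and for stage 2 the synopsis, Protocol 13.15 and SAP 6.5 already require it. Protocol 13.1 and SAP 6.6 also describe the date as an approximate estimate. The intent seems clear too: the SAP version log records a rewording of 6.6 towards the all-responder rule, and the futility text speaks of waiting for all 40 subjects to be evaluable for a confirmed response.

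This shows that a sponsor can comply sensibly. It does not settle which rule governs. The section named for cut-off dates carries the narrower one, and describing the date as approximate leaves the timing of the primary analysis to judgement in an open-label trial.

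Three stronger readings are tempting and are not supported:

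- **That the conflict threatens the type I error.** An undercount can only make rejection harder.
- **That true responders are certain to be lost.** A first response at week 28 is unconfirmed and may never be confirmed at week 36. The group must also meet the timing conditions above.
- **That a wrong, irreversible futility stop is in prospect.** The SAP log refers to a steering committee at stage 1, the synopsis records the last enrolled subject starting on 27 December 2019, and the study goes on to an extension. Stage 1 therefore appears to have been passed.

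**Conclusion.** The inconsistency is real and should be corrected. It is a conflict between stated rules on the primary endpoint, and following the narrower one literally can undercount confirmed responses at the stage 2 test. The likely size is modest. Each true responder left uncounted costs roughly 6 to 7 points of power at a 45% rate (79.8% to 73.5% to 66.2%), but the number uncounted rests on assumptions about late response and accrual that the documents cannot confirm. It may well be zero. The direction is conservative, so a positive result would not be called into question on this ground; a narrow miss could be. For stage 1 the change is now a matter of consistency only.

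**What to change.** Adopt the synopsis rule in Protocol 13.1, Protocol 13.15 (futility), SAP 6.5 (stage 1) and SAP 6.6: the cut-off falls once all subjects of the stage have had the opportunity for four post-baseline assessments and every subject with an unconfirmed CR or PR has had the opportunity for a confirmation scan. Delete the last-subject sentence in all four places.

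The change is to wording only. Sample size, bounds and visit schedule are unaffected. The analysis may move by up to about 8 to 9 weeks, and only if an unconfirmed response is open at the last subject's fourth scan. Counting from the last recorded start, 27 December 2019 plus 36 weeks (252 days) is 4 September 2020, before the Main study period ends on 27 December 2020, so no extra follow-up is needed.
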